**Glossary of Abbreviations**

ASNR= American Society of Neuroradiology  
ADC= apparent diffusion coefficient  
DWI= diffusion-weighted imaging  
fMRI = functional MRI  
MUSE= multiplexed sensitivity encoding algorithm  
QIBA= Quantitative Imaging Biomarkers Alliance  
SCC= squamous cell carcinoma  
WIP= work in progress

**Protocol Revisions History**

Version	20May2020
	24Aug2020
	27Jan2021
	7Apr2021
	2Feb2023
	8Feb2023
	5June2023

## 1.0 BACKGROUND AND RATIONALE

Head and neck tumors can be a significant imaging diagnostic challenge. Anatomic imaging alone is insufficient to differentiate between post-treatment change and recurrent tumor, as both demonstrate increased T2/FLAIR signal and enhancement. Diffusion-weighted sequences (DWI) is a more sensitive and specific sequence that can be used to evaluate this tumor, and that can more easily differentiate between residual/recurrent tumor and post-treatment change (Vandecaveye, 2007). Metabolic imaging with FDG PET/CT is impacted by false-positives in the setting of inflammation or post-radiation necrosis and thus, data must be acquired 8-12 weeks post-treatment to avoid this pitfall. Moreover, PET/CT imaging is less available compared to MRI or CT. MRI does not require ionizing radiation, which is an important factor in head and neck squamous cell cancer patients, as they have an increased risk of secondary tumors such as lung cancer.

MRI systems that include diffusion-weighted imaging (DWI) and apparent diffusion coefficient (ADC) measurements hold promise to facilitate differentiation of tumor recurrence from post-treatment changes and associated complications, since areas of tumor demonstrate restricted diffusion and post-treatment changes do not [Chawla, 2009; Friedrich, 2008; Hermans, 2010; Jansen 2010; King, 2010 and 2013; Maeda, 2008; Mudana, 2018; Perrone, 2011; Vandecaveye, 2007 and 2010]. However, there are multiple pitfalls associated with conventional DWI related to artifacts such as fat saturation, distortion, aliasing/ghosting and spatial resolution. These limit the utility of this technique.

We propose a longitudinal study evaluating post-treatment changes in patients with squamous cell carcinoma (SCC) of the neck using an **innovative optimized DWI pulse sequence to identify more accurately recurrent tumors as well as early non-responders to therapy**.

[figure not shown]
Our optimized DWI pulse sequence includes a combination of new improvements in data acquisition—, specifically multiband echo planar imaging (MultiBand, Siemens Medical Solutions, Erlangen, Germany) and multi-segment K-space readout algorithm (RESOLVE, Siemens Medical Solutions, Erlangen, Germany), i.e. SMS/RESOLVE WIP 1051a. The multiplexed sensitivity encoding algorithm (the MUSE method pioneered by [name] of the University of Arizona, Figure 1) is applied at post processing. Our optimized DWI sequence follows QIBA-recommended guidelines. We found that our DWI pulse sequence improved quantitative artifact parameters [[name], 2019] which in turn should increase the diagnostic accuracy of our technique.

We plan to enroll 60 biopsy-proven neck SCC patients after treatment with surgery, radiation or chemo-radiation. The Otolaryngology, Head and Neck Surgery physicians and their clinic staff will coordinate enrollment. The patients will undergo an optimized research neck DWI protocol up to 3 weeks post-treatment and then a standard-of-care 3-6 months post-treatment FDG PET/CT examination. The optimized research DWI images will be acquired on a dedicated research Siemens 3T Scanner belonging to Washington University's Center for Clinical Imaging Research. The standard-of-care FDG PET/CT will be acquired at one of the Siemens Biograph clinical **PET/CT units located throughout the Barnes-Jewish Hospital Systems that adhere to QIBA FDG PET/CT protocols**. We will compare the ADC values (ADCmin and ADCmean) from the optimized DWI pulse sequence to FDG PET SUVmax. We will follow patients for 1 year to assess their clinical outcomes, including histological results associated with re-biopsy or surgery.

## 2.0 OBJECTIVES

The Specific Aim of this application is as follows: To compare SUVmax and ADCmean/min values to assess the capability of the new DWI pulse sequence to differentiate post-treatment change from residual or early recurrent tumor.

Hypothesis: The optimized research DWI pulse sequence obtained up to 3 weeks post treatment will accurately identify residual/recurrent tumor, as confirmed by the clinical FDG PET/CT obtained at 3-6 months. This would potentially result in a modification of imaging follow-up algorithms, increased cost-savings and eliminate radiation exposure to patients inherent in PET/CT. This would also result in earlier changes to treatment regimens and stratify patients into more or less aggressive tumor response to treatment. The gold-standard will be histological tissue where available and/or 1-year clinical and imaging outcomes, including imaging outcome measurements such as RECIST 1.1 [De Bree, 2017], PERCIST [Joo Hyun, 2016] and iRECIST [Persigehl, 2020].

**Figure 1:** DWI data obtained from a healthy volunteer with a GE 3 Tesla system and eight-channel neurovascular array coil. Single-shot EPI-based DWI was obtained: matrix size = 128  $\times$  128; parallel imaging acceleration factor = 2; field of view = 24 cm  $\times$  24 cm; b-value = 1000 s/mm^2. B, High-resolution DWI data obtained with four-shot interleaved EPI pulse sequence (matrix size = 256  $\times$  256; field of view = 24 cm  $\times$  24 cm; b-value = 1000 s/mm^2) and reconstructed with our developed MUSE algorithm.

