## 3.0 PARTICIPANT SELECTION

### ELIGIBILITY CRITERIA

#### Inclusion Criteria:

- 1) Histologically-proven newly diagnosis or recurrence as indicated by tissue diagnosis of T3 or T4 squamous cell carcinoma of the head and neck
- 2) Must have had or be scheduled for standard-of-care surgical resection, radiation, and/or chemo-radiation of the diagnosed squamous cell carcinoma of the head and neck
- 3) At least 18 years of age
- 4) Patient must be able to understand and willing to sign a written informed consent document.

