## **4.0 STUDY PROCEDURES**

### **IMAGING PLAN**

Overview: 60 biopsy-proven neck SCC patients after treatment with surgery, radiation or chemo-radiation will be enrolled for this trial. The Otolaryngology, Head and Neck Surgery physicians and their clinic staff will assist in coordinating enrollment. The patients will undergo an optimized research neck DWI MRI, up to 3 weeks post-treatment and then a standard-of-care 3-6 months post-treatment FDG PET/CT examination. (\*\*Note: Patients who do not undergo SOC PET/CT at the 3-6 month time point will be considered inevaluable and will be replaced.) Patients who sign the consent form but do not have the MRI will not be considered accrued on this study. The optimized DWI images will be acquired on a dedicated research Siemens 3T Scanner belonging to Washington University's Center for Clinical Imaging Research. The standard-of-care FDG PET/CT mages will be acquired at one of the Siemens Biograph clinical PET/CT units located throughout the Barnes-Jewish Hospital Systems. We will compare the ADC values (ADCmin and ADCmean) to the optimized DWI sequence to FDG PET

SUVmax. For up to 1 year post-treatment, patients' medical records will be reviewed after scheduled SOC visits to additionally assess for clinical outcomes.

	Baseline	up to 3 Weeks Post-Treatment	3-6 Months Post-Treatment	Follow up for up to 1 year post-treatment
Screening	X			
Enrollment	X			
Medical Record Review	X	X	X	X
DWI MRI		X		
FDG PET/CT			SOC	

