### Clinical Data to be Collected

**The following clinical data points will be collected and recorded in REDCAP (Please see attached data sheet):**

- Age
- Birth Gender
- Original Cancer Stage
- Date of original diagnosis
- Cancer Location
- Cancer Stage
- HPV Status
- Cancer Treatment (choice=Surgery)
- Cancer Treatment (choice=Chemotherapy)
- Cancer Treatment (choice=Radiation)
- Surgery Date
- Radiation Dosage
- Chemotherapy Type/Dosage
- Chemotherapy treatment range
- Date of Completion of Initial Treatment
- Smoking Pack Year History
- Date of Study MRI
- Why enrolled?
- MRI Imaging uploaded
- Biopsy Obtained
- Pathology confirms recurrence
- Date of recurrence diagnosis
- Length of time from MRI to clinical/radiographic progression
- Last clinical F/U
- Last imaging F/U
- Treatment after repeat biopsy/surgery

**Duration of Imaging:** MRI data to include anatomical MPRAGE volumetric T1, fat-saturated T2-weighted image (for anatomical localization and cystic/necrotic changes) and optimized research DWI sequence will be acquired in 30 minutes. If at any time the constraints of this protocol are considered detrimental to the patient's health and/or the patient no longer wishes to continue

imaging, the protocol should be discontinued and the reason(s) for discontinuation documented in the case report forms.

**Post-imaging:** While there are no anticipated problems during the research imaging, continuous monitoring for any adverse events or abnormal events will occur during imaging. Once the research MRI is complete, the subject will be asked by a member of the study team how they are feeling prior to leaving the CCIR. If for any reason, the subject is feeling abnormal, [name] or [name], the on-site neuroradiologist, will be notified and will address any adverse events.

**Patient Compensation:** Subject will receive \$100 at the completion of their research DWI MRI imaging. Subjects will be provided compensation by check.

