## 7.0 STATISTICAL CONSIDERATION

### STATISTICAL ANALYSIS

Study Design and Endpoints: This is a pilot study designed as a paired, prospective, single-blinded study in which we compare the sensitivity and specificity of the optimized DWI sequence ADCmean/min versus FDG PET/CT SUVmax for the evaluation of recurrent SCC in post-treatment patients. The primary endpoints of sensitivity and specificity will evaluate the diagnostic accuracy of the optimized DWI sequence ADCmean/min versus the standard-of-care FDG PET/CT SUVmax. The secondary endpoint will evaluate if the enhanced DWI sequence can more expediently assess non-responders to treatment as compared to FDG PET/CT.

Aim 1: The 60 subject sample size for this pilot study was chosen for feasibility of recruitment based on the approximately 650 PET/CT exams performed for head and neck tumor in 2018. ROI will be used for statistical assessments of ADC measurements (see methodology of ADC measurement, above). FDG-PET SUVmax results will be used as the reference standard for tumor or non-tumor tissue. ADCmean, ADCmin and standard deviation will be used to describe distribution of ADC measurements (AADC) in tumor and non-tumor tissues and independent sample t-test will be used to compare ADC measurements between the two groups. Mean difference and 95% confidence interval around that will be used to interpret our results. For ROC analysis, the area under the curve (AUC) will be calculated and the Youden's J index will be used to identify the value of the predictor variable that optimized sensitivity and specificity. Youden's J index varies from 0-1. The threshold value that provides the value of the J index closer to 1 is the value with the best performance and discriminative power. PPV and NPV will also be evaluated. The logistic regression model allows for evaluating this impact after controlling for potential confounders. We will explore the linearity assumption of relationship of delta ADC with logit of outcome (response to treatment) and if the assumption is violated,

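### The gold standard names RECIST 1.1, PERCIST and iRECIST without providing for them, and Section 7.0 makes the comparator PET its own reference standard

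*Combined protocol and SAP*

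**What the plan says.** Section 2.0 defines the reference as histology, where there is any, and/or "1-year clinical and imaging outcomes, including imaging outcome measurements such as RECIST 1.1". PERCIST and iRECIST follow in the same list. The hypothesis in the same section also speaks of the DWI result being confirmed by the 3-6 month clinical PET/CT.

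The Imaging Plan in Section 4.0 schedules an "optimized research neck DWI MRI, up to 3 weeks post-treatment and then a standard-of-care 3-6 months post-treatment FDG PET/CT examination". The schedule table has no imaging in the baseline column. After the PET, "medical records will be reviewed after scheduled SOC visits to additionally assess for clinical outcomes", for up to 1 year. Patients may enter before or after treatment: "Must have had or be scheduled for standard-of-care surgical resection, radiation, and/or chemo-radiation".

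The clinical data list in Section 4.0 includes biopsy, pathology-confirmed recurrence, recurrence date, last clinical and last imaging follow-up, and "Length of time from MRI to clinical/radiographic progression". It prints no lesion diameter, no pre-treatment SUV and no response category. The list refers to an attached data sheet that is not part of the text available here. The MRI guidelines plan ADC measurements only. The PET/CT guidelines plan one SUVmax reading, in the region copied from the ADC evaluation.

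Section 7.0 compares the sensitivity and specificity of ADC with those of PET SUVmax. It also names PET SUVmax as the reference that separates tumor from non-tumor. It names no other reference and does not mention the three response criteria. Its logistic model takes response to treatment as the outcome, without defining it.

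**The concern.** There are two linked gaps.

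First, the three response criteria grade change against an earlier measurement. That is general method knowledge; the protocol does not define them. The plan names the criteria but not which one governs, which scans feed it, who reads them, or how a category becomes tumor or non-tumor. For patients without histology, this part of the reference is left to judgement after the fact.

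Second, the only scheduled PET is one of the two tests being compared. If PERCIST, or imaging outcome more loosely, is taken from that scan, the comparator helps to define the truth it is scored against. Section 7.0 goes further and makes its SUVmax the reference outright.

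At stake is the primary endpoint. A test scored against itself has perfect sensitivity and specificity, and the other test is charged with every PET error as well as its own. The bias runs against the sequence that the study is meant to evaluate.

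**Working it through.** There is no stated figure to reproduce. The sample of 60 was chosen for feasibility, and the plan gives no prevalence, accuracy or histology rate. The check is first a comparison of sections, then an illustration on assumed inputs.

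**Sections side by side**

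- Earlier measurement for a change-based response: none is scheduled (Section 4.0 table), and none is in the printed data list.
- Later measurement: one MRI, on which ADC is measured, and one PET, on which SUVmax is measured. No lesion size is planned on either.
- Reference in Section 2.0: histology and/or 1-year clinical and imaging outcomes.
- Reference in Section 7.0: PET SUVmax.
- Comparator in Section 7.0: PET SUVmax.

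The last three lines cannot all stand. If Section 7.0 is followed, PET sensitivity and specificity are both 100% whatever the data show, and the paired difference is simply DWI's disagreement with PET.

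**Patients who depend on the non-histology part.** If 20-40% have histology (assumed), the number without it is 60 × (1 − 0.40) = 36 to 60 × (1 − 0.20) = 48.

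**Illustration of the bias.** Assumptions: prevalence *p* of 0.2 to 0.4; both tests with the same true sensitivity and specificity *s*, 0.80 or 0.90; errors of the two tests independent given the truth. The true difference is 0.

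With PET as reference for everyone:

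- Apparent DWI sensitivity = [p·s² + (1−p)(1−s)²] / [p·s + (1−p)(1−s)]
- Apparent DWI specificity = [(1−p)·s² + p(1−s)²] / [(1−p)·s + p(1−s)]

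For p = 0.2, s = 0.8: sensitivity = (0.128 + 0.032) / (0.16 + 0.16) = 0.500, and specificity = (0.512 + 0.008) / (0.64 + 0.04) = 0.765. PET scores 1 on both.

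With PET as reference for a random half and the truth for the other half, the reference-positive share for the same inputs is 0.5 × 0.20 + 0.5 × 0.32 = 0.26. PET sensitivity is (0.08 + 0.16) / 0.26 = 0.923, DWI sensitivity is (0.08 + 0.08) / 0.26 = 0.615, and the difference is −0.308.

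| p | s | DWI sens., PET reference for all | DWI spec., PET reference for all | DWI − PET sens., all | DWI − PET sens., half |
|---|---|---|---|---|---|
| 0.2 | 0.80 | 0.500 | 0.765 | −0.500 | −0.308 |
| 0.2 | 0.90 | 0.654 | 0.878 | −0.346 | −0.196 |
| 0.3 | 0.80 | 0.579 | 0.742 | −0.421 | −0.235 |
| 0.3 | 0.90 | 0.735 | 0.864 | −0.265 | −0.141 |
| 0.4 | 0.80 | 0.636 | 0.714 | −0.364 | −0.190 |
| 0.4 | 0.90 | 0.786 | 0.845 | −0.214 | −0.110 |

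If the two tests tend to err on the same patients, the apparent DWI deficit is smaller than shown.

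**The case against.** The strongest reply is that the gold standard does not rest on the response criteria. They are introduced as examples, beside histology and 1-year clinical outcomes. Record review runs from baseline to 1 year, so standard-of-care scans before and after treatment could be retrieved. Radiographic progression and last imaging follow-up are recorded, and the attached data sheet may hold more. A later clinical PET would not be the comparator scan. All of this stands.

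It rules out several stronger readings. A reader might infer that response cannot be derived at all, or that patients without histology have no usable reference. The documents support only that the plan does not provide for it: such scans are neither required nor measured. A reader might also infer that these patients will be classified from the clinical PET impression; no text says so. Nor is the logistic model's outcome beyond derivation. It is undefined, it is nowhere tied to the three criteria, and existing fields can largely supply it.

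One could also argue that the Section 7.0 sentence governs only the ADC group comparison and the ROC analysis, with the paired comparison judged against Section 2.0. That would ease the conflict, but Section 7.0 does not draw this distinction and names no other reference.

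**Conclusion.** The point holds as a gap in provision and a conflict between sections. Section 2.0 names response criteria for which the plan supplies neither the inputs nor a mapping to tumor status. Circularity through PERCIST or imaging outcome is conditional on the study PET being the scan used. Circularity through the Section 7.0 reference sentence is unconditional as written.

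The direction is clear: toward PET and against DWI. The size cannot be computed from the documents. On the assumed inputs above, a true sensitivity difference of 0 would appear as −0.21 to −0.50 if PET is the reference for all patients, and as −0.11 to −0.31 if for half. These ranges, and the 36 to 48 patients without histology, show what is possible; they are not estimates for this study.

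**What to change.** - **Section 2.0:** remove RECIST 1.1, PERCIST and iRECIST from the gold standard. Report them descriptively, only in patients who have a pre-treatment clinical scan.
- **Sections 2.0 and 7.0:** state one identical binary reference. Tumor is pathology-confirmed recurrence, or clinical or radiographic progression by 1 year established by something other than the 3-6 month study PET. Non-tumor is neither of these by 1-year follow-up.
- **Section 7.0:** replace the sentence that makes SUVmax the reference standard, and use the same binary variable as the outcome of the non-responder logistic model. This supplies the outcome only. The model's predictor, change in ADC, still needs a second ADC measurement that the schedule does not contain.
- **Data list:** add one item recording what established each progression. The present field does not show whether it was the study PET, and the last imaging follow-up could be that same scan.

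The cost is an amendment to the wording, one data item and a rule for applying it. The pathology, recurrence, progression and follow-up fields already exist, and no scan is added. Graded response categories are lost as a reference. Patients with PET-only progression that is never confirmed, or with incomplete 1-year follow-up, have to be shown as unclassified or handled in a sensitivity analysis, which will reduce the number in the primary comparison.

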## 3.0 PARTICIPANT SELECTION

### ELIGIBILITY CRITERIA

#### Inclusion Criteria:

- 1) Histologically-proven newly diagnosis or recurrence as indicated by tissue diagnosis of T3 or T4 squamous cell carcinoma of the head and neck
- 2) Must have had or be scheduled for standard-of-care surgical resection, radiation, and/or chemo-radiation of the diagnosed squamous cell carcinoma of the head and neck
- 3) At least 18 years of age
- 4) Patient must be able to understand and willing to sign a written informed consent document.

#### Exclusion Criteria:

- 1) Contraindications to MRI, including:
  - a. MRI-incompatible implantable devices
  - b. severe claustrophobia; and
- 2) Pregnant and/or breastfeeding, with women of childbearing potential having a negative urine or serum pregnancy test

Inclusion of Women and Minorities: Both male and female patients and members of all races and ethnic groups are eligible for this trial.

## **REGISTRATION PROCEDURES**

**Patients must not start any protocol intervention prior to registration through the Siteman Cancer Center.**

The following steps must be taken before registering patients to this study:

- 1) confirmation of patient eligibility;
- 2) registration of patient in the Siteman Cancer Center database;
- 3) assignment of unique patient number (UPN). The research coordinator(s), [name] and/or [name] will perform these tasks and obtain consent form the patients

### **Confirmation of Patient Eligibility**

Confirm patient eligibility by collecting the following information:

- 1) the patient's physician's name;
- 2) the patient's race, sex, and date of birth;
- 3) three letters (or two letters and a dash) for the patient's initials;
- 4) a copy of the signed consent form;
- 5) a completed eligibility checklist, signed and dated by a member of the study team;
- 6) a copy of the appropriate source documentation confirming the patient's eligibility. [name] and/or [name] will perform these tasks and obtain informed consent from the patients.

Both men and women and members of all races and ethnic groups are eligible for this trial.

### **Assignment of UPN**

Each patient will be identified with a unique patient number (UPN) for this study. All data will be recorded with this identification number on the appropriate CRFs.

## **4.0 STUDY PROCEDURES**

### **IMAGING PLAN**

Overview: 60 biopsy-proven neck SCC patients after treatment with surgery, radiation or chemo-radiation will be enrolled for this trial. The Otolaryngology, Head and Neck Surgery physicians and their clinic staff will assist in coordinating enrollment. The patients will undergo an optimized research neck DWI MRI, up to 3 weeks post-treatment and then a standard-of-care 3-6 months post-treatment FDG PET/CT examination. (\*\*Note: Patients who do not undergo SOC PET/CT at the 3-6 month time point will be considered inevaluable and will be replaced.) Patients who sign the consent form but do not have the MRI will not be considered accrued on this study. The optimized DWI images will be acquired on a dedicated research Siemens 3T Scanner belonging to Washington University's Center for Clinical Imaging Research. The standard-of-care FDG PET/CT mages will be acquired at one of the Siemens Biograph clinical PET/CT units located throughout the Barnes-Jewish Hospital Systems. We will compare the ADC values (ADCmin and ADCmean) to the optimized DWI sequence to FDG PET

SUVmax. For up to 1 year post-treatment, patients' medical records will be reviewed after scheduled SOC visits to additionally assess for clinical outcomes.

	Baseline	up to 3 Weeks Post-Treatment	3-6 Months Post-Treatment	Follow up for up to 1 year post-treatment
Screening	X			
Enrollment	X			
Medical Record Review	X	X	X	X
DWI MRI		X		
FDG PET/CT			SOC	

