## **MRI PROCESSING GUIDELINES**

**Overview:** All MRI studies will be blindly evaluated by at least two experienced neuroradiologists (Drs. [name] and [name]). If there is an urgent or emergent finding obtained by the research MRI study, this will be communicated by one of the neuroradiologists directly to the ENT physician for follow up who is caring for the patient, as per normal departmental protocol. In the case of this study, incidental findings are defined as anything not already noted in the medical record.

**Methodology of MRI Evaluation:** The research MRI study of the head and neck will be performed on a Siemens 3T MRI Scanner system located in the Center for Clinical Imaging Research (CCIR). Multiplanar / multisequence MRI data including the optimized research DWI sequence will be acquired. MRI subjects must complete an MRI screening evaluation form before entering MRI zone 3 or the scanning room. Images will be anonymized and sent to CNDA for archiving after diagnostic reports are complete. All anonymized MRI studies will then be blindly evaluated by at least two experienced neuroradiologists (Drs. [name] and [name]). MUSE image processing will be applied post-acquisition.

**Methodology of ADC Evaluation:** The primary tumor, suspicious lesion, and/or area of post-treatment change will be first identified in the anatomical images and then outlined in the ADC sequence by experienced neuroradiologists (Drs. [name] and [name]), excluding areas of cystic change and necrosis. If there are multiple lesions, only the dominant lesion with the lowest ADC will be utilized for analysis, akin to RECIST criteria. If there is geometric distortion, a region of interest will be placed in the undistorted region only. A histogram analysis method will be used to examine the distribution of ADC values within each region of interest (ROI). Only measurable disease defined as a primary tumor, a suspicious lesion, and/or an area of post-treatment change measuring at least 0.5 cm in two perpendicular dimensions will be used. Technically poor or non-diagnostic MR images will be excluded. ADCmean/min will be computed.

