## PET/CT IMAGING PROCESSING GUIDELINES

Overview: When the PET/CT is ordered as a clinical workup, a diagnostic report will be issued by the Nuclear Medicine Department faculty. Neither [name] nor [name] will participate in the preparation or issuing of this report.

Methodology of SUV Evaluation: Anonymized FDG PET/CT data from CNDA will be uploaded into a MIM workstation (MIM Software Inc., Cleveland, Ohio). Fused MPRAGE/DWI images will be used. The region of interest chosen for the evaluation of ADC values will be copied onto the FDG CT/PET, and the SUVmax will be measured. While there is significant variability in SUV measurements [Kinehan, 2010], the reported literature suggest SUVmax > 9.0 -with interquartile range (IQR) 7.4–13.9 and range of 1.5-20.1 - is diagnostic of squamous cell carcinoma [Schwartz, 2004; Morand, 2018] for the primary mass and >4.5 for nodal tumor [Paidpally, 2012]. PET/CT studies are standard of care and are reported as clinical studies.

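### Only the MRI reading is blinded; where tissue is lacking, 1-year tumor status comes from open record review, which can bias the DWI-versus-PET difference in either direction

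*Combined protocol and SAP*

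**What the plan says.** **Blinding.** Section 7.0 states: "This is a pilot study designed as a paired, prospective, single-blinded study". It does not say who is blinded, or to what. The MRI Processing Guidelines supply the only blinded step: "All MRI studies will be blindly evaluated by at least two experienced neuroradiologists". What is withheld from those readers is not stated. The PET/CT guidelines add a partial separation: two named people, presumably the MRI readers, are kept out of the clinical PET report (neither "will participate in the preparation or issuing of this report").

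**Reference standard.** Section 2.0 says: "The gold-standard will be histological tissue where available and/or 1-year clinical and imaging outcomes", "including imaging outcome measurements such as RECIST 1.1", and goes on to list PERCIST and iRECIST. The reference list shows PERCIST to be a PET response criterion. Section 7.0 says something different: "FDG-PET SUVmax results will be used as the reference standard for tumor or non-tumor tissue".

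**Source of the 1-year outcome.** For up to a year after treatment, patients' "medical records will be reviewed after scheduled SOC visits to additionally assess for clinical outcomes" (section 4.0, Imaging Plan).

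**What may be known at that point.** PET/CT is standard of care and reported clinically. Urgent or emergent MRI findings go to the ENT physician (MRI Processing Guidelines). Clinically significant incidental findings, including new tumor, go to the treating physician through the Principal Investigator (section 5.9). The MRI guidelines define an incidental finding as one not already in the medical record, so a suspected recurrence that has not yet been charted would qualify.

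**The concern.** The primary endpoints are sensitivity and specificity, and the primary comparison is the DWI-minus-PET difference in each, with a 90% confidence interval. Both depend on who is labeled as having tumor. For patients without tissue, the label is a judgment made from records, and the plan puts no barrier between that judgment and the results of the two tests being compared.

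If doubtful cases are settled in line with one test, that test's errors are partly relabeled as correct calls (review bias). If PERCIST is scored on the study PET, that PET becomes part of its own reference (incorporation bias). A confidence interval reflects neither. The two tests are also not equally exposed: PET is in the clinical record as a matter of course, whereas MRI findings reach the treating physician only by the routes above.

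**Working it through.** The plan gives no figure to reproduce. The sample of 60 was set by feasibility, with no prevalence, effect size or power. What follows is illustration only. Every input except N = 60 and the 90% level is an assumption.

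**A. Doubtful cases settled toward DWI.** Assume 18 tumors and 42 non-tumors, with true sensitivity and specificity of 0.75. Then TP = 13.5, FN = 4.5, TN = 31.5 and FP = 10.5. A share *f* of patients is doubtful, at random with respect to truth, and takes the DWI result as its label. Only the errors change cell.

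- Sensitivity = (TP + f·FP) / (TP + f·FP + (1 − f)·FN)
- Specificity = (TN + f·FN) / (TN + f·FN + (1 − f)·FP)
- f = 0.10: 14.55/18.60 = 0.78 and 31.95/41.40 = 0.77; relabeled patients 0.10 × 15 = 1.5
- f = 0.20: 15.6/19.2 = 0.81 and 32.4/40.8 = 0.79; relabeled patients 0.20 × 15 = 3

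**B. Doubtful cases settled toward PET.** Assume both tests have true sensitivity and specificity of 0.80, errors are independent given true status, prevalence π is 20-40%, and the doubtful share d is 10-30%.

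- Labeled tumor: L = (1 − d)π + d·P(PET+), where P(PET+) = 0.8π + 0.2(1 − π)
- PET sensitivity = [(1 − d)·0.8π + d·P(PET+)] / L
- DWI sensitivity = [(1 − d)·0.8π + d·P(both+)] / L, where P(both+) = 0.64π + 0.04(1 − π)

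Worked case, π = 0.20 and d = 0.30: P(PET+) = 0.32, P(both+) = 0.16 and L = 0.14 + 0.096 = 0.236. PET sensitivity is (0.112 + 0.096)/0.236 = 0.881 and DWI sensitivity is (0.112 + 0.048)/0.236 = 0.678. The gap is 0.203, although the true gap is zero.

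| π | d | DWI sens. | PET sens. | False gap |
|---|---|---|---|---|
| 0.20 | 0.10 | 0.755 | 0.830 | 0.075 |
| 0.20 | 0.30 | 0.678 | 0.881 | 0.203 |
| 0.30 | 0.10 | 0.773 | 0.825 | 0.052 |
| 0.30 | 0.30 | 0.722 | 0.870 | 0.148 |
| 0.40 | 0.10 | 0.782 | 0.822 | 0.040 |
| 0.40 | 0.30 | 0.748 | 0.864 | 0.116 |

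Over the same range the false specificity gap is about 2 points (0.817 − 0.797) to 8 points (0.857 − 0.776), also against DWI. The number of patients relabeled is 60 × 0.20 × d, or 1.2 to 3.6.

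**C. Scale against sampling error.** The 90% half-width for one sensitivity of 0.80 is 1.645·√(0.16/n): 0.19 for 12 tumors and 0.13 for 24. For the paired difference under the independence assumed in B, it is 1.645·√(2 × 0.16/n): 0.27 for 12 tumors and 0.19 for 24. The bias ranges from small to a sizable part of the interval's half-width.

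**D. If section 7.0's reference applied instead.** With SUVmax as the reference, PET agrees with itself at the reference cut-off, so its sensitivity and specificity are 100% by construction. The record review would then not set status, and the DWI-versus-PET difference would carry no information about PET's accuracy. The comparison needs the section 2.0 reference, and that is where unblinded assignment matters.

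**The case against.** The strongest reply is that the documents do not show DWI results to be open. Section 5.9 says the research MRI is not a clinical examination. The listed clinical data items include the MRI date and an upload flag, but no ADC value, MRI read or SUVmax. The MRI guidelines mention diagnostic reports without saying that they enter the chart. Moreover, section 7.0 derives the ADC cut-off from Youden's index, which needs tumor status first, so no ADC-positive or ADC-negative call exists for an assessor to follow. All of this stands. A reader might infer that the assessor sees the ADC results; the documents support only that PET reports, and MRI findings passed to the treating physician, may be known. A relayed suspicion of tumor can still influence a label without any ADC cut-off.

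It also stands that illustration A, taken alone, is one-sided. PET is the test documented as being in the record, and following PET harms DWI. Both illustrations move fewer than four patients, within sampling error for a pilot of this size. But that error is shown by the interval, and the bias is not.

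Two further inferences go beyond the text. One is that a negative biopsy ends verification early: section 2.0's wording permits that reading, but the Imaging Plan reviews records for up to a year without exempting biopsied patients. The other is that tissue will come mainly from test-positive patients: this is plausible, but not stated.

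Finally, under section 7.0's reference the record review decides nothing, so blinding it would not cure the larger problem in D. That is correct, and it sets the order of the fix.

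**Conclusion.** The point holds as a cheap improvement. The plan blinds the MRI reading and nothing else that it describes. Under the section 2.0 reference, patients without tissue are classified by open record review, with no named assessor, no blinding and no rule for doubtful cases, while PET results and relayed MRI findings may be known.

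The size is illustrative. Following DWI, an assumed sensitivity of 0.75 becomes about 0.78-0.81 with 10-20% doubtful. Following PET, two tests that are both truly 0.80 show a false sensitivity gap of about 4-20 points with 10-30% doubtful. These figures rest on assumed prevalence, accuracy, doubtful share and, for the second, independent errors. The documents do not settle which direction would prevail, so a conclusion that the plan favors DWI is not supported. The point is secondary to the conflict between sections 2.0 and 7.0 over the reference standard.

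**What to change.** First, reconcile sections 2.0 and 7.0 so that tissue or 1-year outcome, not SUVmax, sets tumor status for the primary comparison. Then add to sections 4.0 and 7.0:

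> Tumor status at 12 months is assigned from record extracts by existing study staff not involved in the MRI reads, with ADC values, the research MRI read and the study SUVmax withheld, and is locked before ADC and SUVmax are linked. Sensitivity and specificity are also shown by type of reference (tissue or follow-up).

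The reconciled text should also say whether PERCIST may be scored on the study PET, since blinding alone would not remove that overlap.

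The cost is protocol wording and some preparation of extracts. No scan or visit is added, and the relay of findings to clinicians is untouched. PET results and relayed MRI findings cannot be fully hidden in clinical notes; the plan should state this as a limitation.
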